**4. Purpose, hypothesis and key questions:**

The proposed study will examine the threshold for nicotine self-administration (NSA) using five different nicotine doses in young adult male and female non-dependent smokers (light and intermittent smokers or LITS). We propose a double-blind, placebo-controlled study that will enroll 195 individuals, targeting a total of 72 completers (36 male and 36 females). In each of the five experimental sessions, smokers will be randomly assigned to one of the five doses of nicotine (0.0125, 0.025, 0.05, 0.1 and 0.2 mg/70 kg). The highest dose, 0.2 mg/70 kg, corresponds to nicotine delivered by about one or two puffs of a cigarette. At the beginning of each experimental session, smokers will sample the assigned both the nicotine dose for that experimental session, and the placebo (saline) dose, followed by the opportunity to choose between nicotine and placebo for a total of ten choices over a 165-minute period. The main outcomes will be threshold dose (the minimum dose of nicotine that is self-administered more than placebo) and the slope of dose-response for nicotine self-administration (changes in nicotine self-administration per unit change in nicotine dose). We will also collect measures of nicotine intake (cotinine), nicotine clearance (3-hydroxycotinine (3-HC) / cotinine), and self-report drug effects.

The following questions will be addressed:

Aim #1: To assess the threshold reinforcing dose and dose-effect curve for IV NSA at low doses in young adult LITS.

Hypothesis #1A: The threshold reinforcing doses for IV NSA will be between 0.0125 to 0.1 mg/70 kg.

Hypothesis #1B: The dose-effect curve for NSA will differ between males and females with relatively flat curve in female smokers.

Aim #2: To assess the threshold and dose-effect curve for the positive and negative/aversive subjective effects of IV nicotine at low doses and its relationship to nicotine reinforcement.

Hypothesis #2 A: The threshold for the positive effects will be between 0.0125 to 0.1 mg/70 kg, for the negative/aversive effect it will be  $\geq 0.1$  mg/70 kg.

Hypothesis #2B: Nicotine reinforcement will be positively correlated with the positive and negatively correlated with the negative/aversive subjective effects of IV nicotine.

Exploratory Aims: To examine the influence of nicotine clearance rate on nicotine reinforcement threshold and dose-effect curve.

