## **12. Data analysis methods:**

Data analyses: The primary analyses will be intent-to-treat and will include all available data on subjects who complete at least one test day. Mixed-effects models will be used to test the study hypotheses. These models allow for different numbers of observations per subject, use all available data on each subject, and are unaffected by randomly missing data. They also provide flexibility in modeling the correlation structure of the data. All data will be checked for normality and transformations will be applied as necessary. Significance level of 0.05 will be used for the main hypotheses and Bonferroni correction will be applied for post-hoc tests and secondary analyses.

Specific Aim #1: Aim #1: To assess the threshold reinforcing dose and dose-effect curve for IV NSA at low doses in young adult LITS. Hypothesis #1A: The threshold reinforcing doses for IV NSA will be between 0.0125 to 0.05 mg/70 kg. Hypothesis #1B: The dose-effect curve for NSA will differ between males and females with relatively flat curve in female smokers.

**Aim #1 Analysis:** The reinforcing effects of nicotine will be determined by the number of IV NSAs in each session, ranging from 0 to 10. The threshold dose for NSA will be determined by the lowest dose of nicotine for which the number of NSAs is significantly greater than those for placebo (saline) (i.e., proportion of NSA significantly higher than 0.5). For assessing the dose-response relationship, the parameters of interest will be the slope and shape of the dose-response curve. The slope indicates the degree to which self-administration changes with an increase in nicotine dose (in other words, sensitivity of NSA to changes in nicotine dose).

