The analysis of Aim #1 will conducted in several steps. First, we will use descriptive statistics and figures to summarize the data. In particular, the number of NSAs for each dose of nicotine will be plotted individually, for the entire sample, and for male vs. female and smokers. This step will allow a visual inspection of both individual and group differences for estimating the threshold dose and the shape of the dose-response curve for nicotine reinforcement. Second, we will fit mixed effects logistic regression models with the proportion of NSAs per session (out of 10) as the dependent variable, dose as a fixed categorical predictor and subject as a random effect. This approach allows us to take into account the correlations between repeated observations on the same individual and to estimate individual deviations from the overall group thresholds.

It also does not assume a specific form of the dose-response relationship and allows us to use all available data on a subject in the unlikely event that a subject fails to complete a session. If a subject fails to complete a session, the total possible number of self-administrations for this subject and session will be adjusted.

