We expect to observe a significant dose effect and will compare the proportion of NSAs at each dose to 0.5 across subject groups. The lowest nicotine dose that has a significantly higher proportion of NSA than 0.5 will be selected as the threshold dose (Hypothesis 1A). To assess the dose-response relationship in the preference for nicotine, polynomial effects of dose (linear, quadratic, cubic) and change-point linear models will be tested in the mixed effects logistic regression model. We anticipate that there will be a significant linear relationship between dose and response rate at lower doses with flattening of the relationship at higher doses. We will use the slope of the dose effect to assess the linear dose effect. Alternative non-linear dose response relationships will be considered if residual plots reveal significant deviations of the models from linearity. Gender differences in the shape of the curve for NSA will be examined in the logistic regression model by including gender main effect and its interactions with dose (Hypothesis 1B). Significant interactions between the group factors and dose will be considered supportive of systematic group differences in the dose-response relationships between groups. If significant interactions are observed, then separate thresholds and curves will be estimated within each subject group.

**Specific Aim #2:** To assess the threshold and dose-effect curve for the positive and negative/aversive subjective effects of IV nicotine at low doses and its relationship to nicotine reinforcement. Hypothesis #2 A: The threshold for the positive effects will be between 0.0125 to 0.1 mg/70 kg, for the negative/aversive effect it will be  $\geq 0.1$  mg/70 kg. Hypothesis #2B: Nicotine reinforcement will be positively correlated with the positive and negatively correlated with the negative/aversive subjective effects of IV nicotine.

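### The Aim 1 logistic model names subject as its only random effect, so any clustering of choices within a session makes the slope, dose and sex-by-dose tests too liberal

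*Combined protocol and SAP*

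**What the plan says.** Section 12, Aim #1 Analysis, takes the share of nicotine choices among the ten in each session as the response, with "dose as a fixed categorical predictor and subject as a random effect". For an incomplete session, "the total possible number of self-administrations for this subject and session will be adjusted", so each choice counts as one binomial trial.

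The opening of section 12 says of mixed models in general: "They also provide flexibility in modeling the correlation structure of the data". No particular structure beyond the subject effect follows.

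The same framework carries every Aim 1 test:
- each dose's proportion against 0.5, for the threshold (Hypothesis 1A);
- polynomial and change-point dose effects, since "the parameters of interest will be the slope and shape of the dose-response curve";
- gender and its interactions with dose (Hypothesis 1B). If an interaction is significant, "then separate thresholds and curves will be estimated within each subject group".

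Section 4 lists the slope beside the threshold dose as a main outcome.

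**The concern.** A subject random effect allows for correlation that a person carries across all five sessions. It does not allow for choices within one session being more alike than that person's average and the dose would predict. Each dose is given in a single session, so a session effect is the same thing as a subject-by-dose effect.

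The plan itself gives reasons to expect some clustering:
- A and B are labelled at random in each session (section 11.A). A participant who cannot tell the infusions apart but leans towards one label produces session-level clustering, even at an inactive dose.
- Hypothesis 2B expects the response to that session's sample dose to go with that session's choices. The Aim 1 model does not contain that response.
- Estradiol and progesterone are measured before each session as covariates (section 11.C) but do not appear in the Aim 1 model.
- The exploratory aim expects nicotine clearance to influence the dose-effect curve. A random intercept only shifts a person's whole curve up or down.

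The slope and the sex-by-dose interaction rest on within-subject dose contrasts, where an omitted session term matters most. A false interaction would be read as support for Hypothesis 1B and would also split the reported threshold by sex.

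**Working it through.** **1. The plan's own figure.** Section 12, Rationale for sample size, states 80% power for 67% against 50% with 72 subjects, two-sided alpha 0.05. Treat the 72 subjects as single binary units and reject at 45 or more of 72. The exact upper-tail error is 0.022, and power is 0.810 at two-thirds and 0.826 at 0.67. The figure is reproduced. It takes no credit for ten choices per session, so this concern does not undermine it.

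**2. Analytic check.** With ten choices per session, the variance inflation for a within-subject contrast is about φ = 1 + (10 − 1) × ICC. Here ICC is the between-session variance of the true choice probability divided by p(1 − p). Values below average over an assumed subject SD of 0.5 logits, with true preference centred on 0.5.

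| Session SD (logits) | φ | 1-df error = P(χ²₁ > 3.84/φ) | 4-df error = P(χ²₄ > 9.49/φ) |
|---|---|---|---|
| 0.3 | 1.185 | 7.2% | 9.1% |
| 0.5 | 1.483 | 10.8% | 17.1% |
| 1.0 | 2.529 | 21.8% | 44.1% |

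For scale, session SD 0.3 puts 95% of sessions at a true preference of about 36–64%, and SD 0.5 at about 27–73%.

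**3. Why the threshold test suffers less.** On the logit scale near 0.5, the binomial variance of one session is about 1/(10 × 0.25) = 0.40. Session SD 0.3 adds 0.09. That is 0.09/0.40 = 22.5% of what a within-subject contrast allows for. It is only 0.09/(0.40 + 0.25) = 14% of what a dose mean allows for, because the dose mean already carries the subject variance (0.5² = 0.25).

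**4. Simulation of the stated model.** 72 complete subjects (36 per sex), five doses, ten choices, true preference 0.5 at every dose, equal session variance at all doses. Fitting was by maximum likelihood with Gauss-Hermite quadrature, 2000 trials per scenario, Wald tests at 5%. Section 12 does not fix the form of the interaction test, so the 4-df and slope versions are both shown.

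| Type I error (%) at session SD | 0 | 0.3 | 0.5 | 1.0 |
|---|---|---|---|---|
| **Subject SD 0.5** | | | | |
| Dose vs 0.5, two-sided | 5.4 | 6.4 | 7.6 | 13.9 |
| Dose vs 0.5, upper tail (nominal 2.5) | 2.7 | 3.1 | 3.9 | 7.2 |
| Overall slope per mg | 4.4 | 7.8 | 10.6 | 22.8 |
| Dose, 4 df | 5.1 | 9.2 | 16.6 | 45.8 |
| Sex-by-slope per mg | 4.5 | 7.0 | 10.1 | 20.8 |
| Sex-by-dose, 4 df | 5.0 | 9.6 | 17.2 | 46.3 |
| **Subject SD 1.0** | | | | |
| Dose vs 0.5, two-sided | 5.3 | 5.5 | 7.0 | 10.4 |
| Dose vs 0.5, upper tail (nominal 2.5) | 2.5 | 2.9 | 3.4 | 5.2 |
| Overall slope per mg | 4.5 | 6.6 | 9.2 | 23.2 |
| Sex-by-slope per mg | 5.1 | 7.7 | 10.8 | 22.6 |
| Sex-by-dose, 4 df | 4.2 | 9.0 | 15.8 | 46.5 |

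Monte Carlo standard errors are 0.2–0.4 points for the per-dose rows, 0.5–0.7 for other rates of 5–10%, and 1.1 near 45%. A separately coded simulation agrees: over both subject SDs, 4-df sex-by-dose error was 8.3% at session SD 0.3 and 14.8–16.7% at 0.5, and slope error was 7.7–8.7% and 10.2–11.6%.

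**5. Session variance at effective doses only.** Two doses were given an assumed logit of 0.7, with subject SD 0.5 and session SD 0.3 / 0.5 / 1.0 at those doses alone. Error at null doses is 4.9 / 4.7 / 4.7%. The 4-df sex-by-dose error is 6.6 / 9.0 / 21.2%, and sex-by-slope per mg is 6.7 / 9.2 / 17.1%.

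**6. With a session-within-subject intercept.** In the equal-variance cases: per-dose 4.2–5.8%, 4-df dose 4.5–6.5%, 4-df sex-by-dose 4.3–7.4% (4.6–6.0% in the separate simulation), sex-by-slope 3.6–6.5%, overall slope 4.8–5.8% (subject SD 0.5 only).

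**The case against.** The strongest objection is that this is a conditional risk, not a demonstrated error. With no session variance the stated model is right, and the documents give no value. Session SD 1.0 has no support in them: at subject SD 0.5 it makes session variance four times subject variance. The large overall slope and dose errors also need preference of 0.5 at all five doses, whereas the plan expects a dose effect. All of that stands. SD 0.3–0.5 should be read as the main range and 1.0 as an extreme.

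Second, the threshold, which is the first-named main outcome and the only Aim 1 quantity with a power statement, is little affected. That also stands.

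Third, the wording does not say that the subject effect is an intercept only, and the plan wants to estimate individual deviations from the group thresholds. A subject-level dose effect would be compatible with the text. But none is stated, so the structure is at best incomplete. The residual plots mentioned are for non-linearity, with no stated action on dispersion.

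Fourth, the Bonferroni rule for post-hoc tests may limit false sex-specific thresholds. It would not prevent the false interaction that triggers them.

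**Conclusion.** The concern holds as an under-specified random-effects structure that should be fixed. The direction is certain if sessions cluster, but the size is not known.

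Under equal session variance and the two subject SDs tried, a session SD of 0.3 takes the slope tests to about 7–8% and the 4-df tests to 9–10%, nearly double nominal. At 0.5 these are about 9–11% and 16–17%. If clustering is confined to effective doses, inflation of the sex-by-dose tests is smaller but present, and null-dose tests are not inflated. The threshold's upper-tail error stays at 2.9–3.9% for session SD 0.3–0.5.

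The exposed results are the slope, a named main outcome, and Hypothesis 1B with the rule that splits thresholds by sex. Every variance component here is an assumption, so confidence is medium.

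**What to change.** In section 12, Aim #1 Analysis, state the random effects as subject plus session nested within subject. Base the dose-versus-0.5, polynomial, change-point, slope and sex-by-dose tests on that model.

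As a sensitivity analysis, repeat the sex-by-dose and sex-by-slope tests with subject-clustered robust standard errors and an F or t reference. One common session variance does not fully cover variance that differs by dose. With variance at effective doses only (SD 0.3 / 0.5 / 1.0), the nested model leaves 4-df sex-by-dose error at 5.0 / 6.5 / 7.3% and sex-by-slope per mg at 5.5 / 6.1 / 8.9%, and is conservative at null doses at SD 1.0 (2.4%). The robust tests gave 4.4–5.5% for sex-by-dose with F(4,67) and 4.3–5.8% for sex-by-slope with t(70). A chi-square reference gave 6.2–7.4% for sex-by-dose, so the reference distribution should be stated.

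The cost is one model term and some wording, with no change to procedures or sample size. Power per dose for 67% against 50% is 99.9–100% after the change, at subject/session SDs of 0.5/0.3, 0.5/0.5, 0.5/1.0 and 1.0/1.0.

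The plan states no sex-by-dose power. As an assumed example, let men rise evenly from 50% to 67% over the five doses while women stay at 50%, with subject SD 0.5. At session SD 0 / 0.3 / 0.5 / 1.0, power after the change is 86 / 82 / 74 / 48% (4 df) and 94 / 90 / 86 / 61% (slope per mg). Without clustering the added term costs about 2 points or less (86% against 88%, 4 df).

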#### *Proposed Study*

Although the presumption of an addictive threshold dose of nicotine is one of the pillars of nicotine reduction strategies, it has yet to be characterized in well-designed human studies. This project will address this gap by assessing the threshold and dose-effect curve for NSA over a low dose range that is expected to capture the reinforcement threshold. It is likely that the nicotine reinforcement threshold will display inter-individual differences. Older and dependent smokers, compared to young adult LITS, may likely have higher reinforcement threshold due to tolerance to nicotine's behavioral effects as a result of long-term nicotine intake. We chose young adult LITS given that the threshold for addictive doses of nicotine was estimated based on the nicotine intake of LITS. As suggested by previous findings from our, and other research groups, male and female smokers may differ in their sensitivity to the behavioral effects of nicotine. In addition, there is evidence to suggest that the rate of nicotine clearance may affect nicotine dose-effect curve and reinforcement threshold. Therefore, the influences of both gender and nicotine clearance rate [assessed by the ratio of hydroxycotinine/cotinine or otherwise known as the nicotine metabolite ratio (NMR)] will be examined in this application. This project will also examine the relationship between NSA and the positive and negative/aversive subjective effects of IV nicotine.

These subjective measures are important because evidence suggests that while positive drug effects are associated with abuse liability and drug intake, sensitivity to the negative/aversive subjective effects of nicotine may prevent both the initiation of tobacco product use and the amount of nicotine intake in established tobacco users. Accordingly, nicotine reinforcement may be a function of the relative balance between nicotine's positive and negative/aversive effects. However, to what extent the individual's sensitivity to the negative/aversive effects of nicotine changes the threshold and dose-effect function for nicotine reinforcement has not been determined. Identifying factors that affect the reinforcement threshold of nicotine will be an important step in developing science-based policies for reducing nicotine in tobacco products.

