**Justification for the nicotine doses:** For this proposal, we chose five doses of nicotine that are in low dose range including 0.0125, 0.025, 0.05, 0.1 and 0.2 mg/70 kg. The highest dose, 0.2 mg, is equivalent to the amount of nicotine delivered from one or two puff of a cigarette, which ranges from 0.05 to 0.2 mg/puff or 0.5 to 2.4 mg/cigarette 1.0 - 2.4 mg, delivered via 10 to 13 puffs (33, 81, 82). In our previous study, 0.2 mg/70 kg dose of nicotine produce positive subjective drug effects and were self-administered by male dependent smokers (34). The lowest dose will be 0.0125 mg/70 kg, lower than the amount estimated to be the addictive threshold for nicotine by B&H, 0.17mg nicotine/cigarette or 0.014 mg nicotine/ puff. We also included 3 additional doses of nicotine 0.025, 0.05, 0.1 mg, in between the 0.2 and the 0.0125 mg dose to provide a more detailed assessment of dose-effect function. These five doses of nicotine and placebo should allow for a detailed examination of individual differences in NSA at a low dose range

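### Aim 1 specifies no random dose slope, so the slope and gender-by-dose (H1B) tests exceed 5% if subjects differ in dose sensitivity

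*Combined protocol and SAP*

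**What the plan says.** Section 12, Aim #1 Analysis, describes a mixed-effects logistic regression for the proportion of nicotine choices per session, with "dose as a fixed categorical predictor and subject as a random effect". One stated purpose of the random effect is "to estimate individual deviations from the overall group thresholds".

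The same section then tests dose-response in that framework: "polynomial effects of dose (linear, quadratic, cubic) and change-point linear models will be tested in the mixed effects logistic regression model". On the slope it says: "We will use the slope of the dose effect to assess the linear dose effect". Hypothesis 1B is examined "by including gender main effect and its interactions with dose". A significant interaction counts as support for a group difference and leads to separate thresholds and curves for each group.

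The opening of Section 12 says of mixed models in general: "They also provide flexibility in modeling the correlation structure of the data". It gives no structure and no rule for choosing one. The main hypotheses are tested at 0.05. Section 4 lists the slope of the dose-response as a main outcome.

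**The concern.** Sex is a between-subject factor and each subject is meant to be tested at all five doses. For the slope and for gender-by-dose, the independent unit is therefore the subject's own dose response. If people differ in dose sensitivity, the mean slope of 36 men will differ by chance from that of 36 women by more than binomial noise alone. A model with only a random subject level has no term for this, so its standard error for the slope is too small.

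Such variation is plausible on the plan's own account: Section 5, Proposed Study, says the rate of nicotine clearance may affect the dose-effect curve.

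Two results are at stake. A chance difference between the sexes could be reported as support for Hypothesis 1B, and it would also trigger sex-specific thresholds. The confidence interval for the slope would be too narrow.

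**Working it through.** **The plan's own figure.** Section 12 gives no error rate or power for the slope or for gender-by-dose. Its one Aim 1 figure is 80% power to tell 67% from 50% with 72 subjects. An exact two-sided binomial test (reject at 45 or more of 72) gives 81.0% at two-thirds, so that figure reproduces. It concerns a single proportion against 0.5 and is not affected here.

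**Inputs from the documents.** 36 men and 36 women, five sessions (Section 11.A); doses 0.0125, 0.025, 0.05, 0.1 and 0.2 mg/70 kg, which is four doublings; 10 choices per session (Section 11.E); alpha 0.05 (Section 12).

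**Assumed.** Slope SD s = 0.1, 0.2 or 0.3 logit per doubling; SD of subject level 0.5 logit; no true mean slope or sex difference; all sessions completed. For scale, at s = 0.2 a subject 1 SD above a flat average goes from logit −0.4 (40% nicotine choices) at the lowest dose to +0.4 (60%) at the highest.

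**Closed form, linear tests (1 df).** Score the doses −2 to 2, so the sum of squares is 10.

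- Information on one subject's slope: 10 × 0.25 × 10 = 25. Binomial variance: 1/25 = 0.04, or about 0.042 after allowing for the spread in subject level.
- True variance of a subject's estimated slope: 0.042 + s². The random-intercept model uses 0.042.
- Variance ratio: k = 1 + s²/0.042. Actual test size: 2 × P(Z > 1.96/√k).

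**Closed form, categorical gender-by-dose (4 df).** Only the linear contrast is inflated, so the statistic behaves as k·χ²(1) + χ²(3), compared with the 5% point of χ²(4), 9.488.

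| s | k | √k | 1.96/√k | 1-df size | 4-df size |
|---|---|---|---|---|---|
| 0 | 1 | 1 | 1.960 | 5.0% | 5.0% |
| 0.1 | 1.238 | 1.113 | 1.761 | 7.8% | 6.3% |
| 0.2 | 1.952 | 1.397 | 1.403 | 16.1% | 10.9% |
| 0.3 | 3.143 | 1.773 | 1.106 | 26.9% | 18.6% |

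**Fitted random-intercept logistic models on simulated null trials, nominal 5%.**

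| Test | s = 0.1 | s = 0.2 | s = 0.3 |
|---|---|---|---|
| Gender-by-dose, 1 df (1,600 trials per setting) | 8.4% | 14.6% | 23.5% |
| Gender-by-dose, 1 df (about 1,120 to 1,345 trials) | 9.1% | 16.1% | 24.7% |
| Gender-by-dose, 1 df, likelihood ratio (about 260 to 310 trials) | 7.3% | 13.7% | 25.4% |
| Overall slope, 1 df (1,600 trials) | 8.1% | 14.2% | 24.2% |
| Gender-by-dose, 4 df, categorical (1,600 trials) | 6.8% | 9.6% | 14.6% |

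- At s = 0 the 1,600-trial run gave 4.4% (slope), 5.6% (gender-by-dose, 1 df) and 5.4% (4 df), so the excess comes from slope variation.
- Raising the level SD to 1.0 at s = 0.2 gave 13.9% (slope) and 13.3% (gender-by-dose).
- With dose in raw mg over the same logit range, gender-by-dose ran at 14.5% (1 df) and 9.0% (4 df) at s = 0.2, and at 25.1% and 17.0% at s = 0.3.

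**Remedies under the same nulls (s = 0.1, 0.2, 0.3).**

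- Random intercept and slope with covariance: 4.5%, 3.9%, 5.3% for gender-by-dose and 5.9%, 4.6%, 3.4% for the slope (simulation error about ±2.5 points).
- Subject-clustered robust standard errors, linear gender-by-dose: 5.6%, 4.8%, 5.4%. The robust version of the 4-df test was not simulated.

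**The case against.** **The plan does not exclude a random slope.** It mentions flexible correlation structures and individual deviations from group thresholds. That stands as a limit on wording: a reader might infer that the plan declares slopes common within sex, and it does not. But the only random term it names is subject, and the choice of structure can decide whether Hypothesis 1B is declared.

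**No single inflation figure belongs to this plan.** A reader might infer that the tests run at about 16%. That value needs a slope SD of 0.2 and the linear test, and no slope SD is given anywhere. Hypothesis 1B concerns the shape of the curve, and with categorical dose its test has 4 df and is less inflated. Both points stand, so the size is given as a range for each test.

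**The plan's remarks on individual differences do not establish slope variation.** "It is likely that the nicotine reinforcement threshold will display inter-individual differences" concerns thresholds, and with a common slope different subject levels already produce different thresholds. "These five doses of nicotine and placebo should allow for a detailed examination of individual differences in NSA at a low dose range" may refer to the level of self-administration (NSA). This stands. The clearance remark in Section 5 is better support, though it gives no magnitude.

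**A t-test on per-subject slopes looks like the simple remedy.** In the simulations it holds about 5%. But it drops anyone with one session, whom Section 12 includes, and unweighted it counts a two-session slope as much as a five-session one. It is not recommended here.

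**Conclusion.** The gap holds as one of specification. The Aim 1 model names subject as its only random effect, and the slope and Hypothesis 1B tests are taken from it, so followed as written they leave out between-subject variation in dose sensitivity. For an assumed slope SD of 0.1 to 0.3 logit per doubling, the linear tests run at about 8% to 25%. The categorical gender-by-dose test runs at about 7% to 18%; its upper end lies between the fitted results (14.6% to 17.0%) and the approximation (18.6%). With no slope variation both hold 5%.

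These figures assume that all 72 subjects complete five sessions, and their size rests on a slope SD that the documents do not supply. That the inflation arises whenever slopes vary does not depend on the value chosen.

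**What to change.** In Section 12, Aim #1 Analysis, state that the slope and gender-by-dose tests come from a mixed logistic model with a random intercept and a random dose slope within subject, including their covariance, on the dose scale used for the slope.

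Add that if this model does not converge, or when dose enters as categorical or polynomial terms, the mean model is kept and subject-clustered robust standard errors are used. A linear random slope does not cover individual variation in curvature, which is why the robust option is needed there. This keeps in everyone who completes at least one test day. Name the small-sample correction for the robust 4-df test, since its size was not checked here.

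The cost is a short wording change and two more parameters (a variance and a covariance), with no new data or subjects. If subjects do differ, intervals for the slope and gender-by-dose widen by about √k: 11%, 40% and 77% at slope SDs of 0.1, 0.2 and 0.3, with correspondingly less power for Hypothesis 1B.

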**Aim 2 Analysis:** The subjective-positive effects of nicotine which will be determined by the main dependent variables of scores on the "like the drug" and "want more drug" items of the Drug Effects Questionnaire, ranging from 0 to 100. The negative aversive effects of nicotine will be determined by the "dislike the drug" and "lightheaded/dizzy" item of the DEQ. The analysis for Specific Aim #2A will be similar to the analysis described for Specific Aim #1A except that the dependent variables will be continuous and thus we will use random effects linear regression. Gender effects will be explored also as outlined for Specific Aim #1B. Prior to analysis, we will also assess the distribution of the DEQ items and apply transformations as necessary. Furthermore, the mean ratings at each dose will be compared to 0. To assess the

relationship between nicotine reinforcement and positive subjective effects, and between nicotine reinforcement and negative subjective effects (Specific Aim #2B), we will use mixed effects models with the proportion of NSAs per session as the dependent variable, positive (negative) subjective effects in response to the sample dose as the main predictor of interest (in separate models for positive and negative effects). Nicotine dose, gender and the interactions among subjective effects, dose and gender will also be assessed. Non-significant interactions will be dropped from the models via backward elimination subject to the constraint that the models will be hierarchically well-formulated at each step. Statistically significant associations between subjective effects and NSA across doses and gender are expected but we will also explore whether these relationships vary by gender and dose.

**Exploratory Aim #1:** To examine the association between baseline 3HC/cotinine ratio and nicotine reinforcement threshold. To test this hypothesis, correlation analysis including 3 HC/cotinine ratio and nicotine reinforcement threshold will be performed in the total sample as well as in subgroups (male vs. female smokers).

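### Hypothesis 2A expects one threshold per construct, but the analysis yields one for each of two DEQ items and does not say which decides

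*Combined protocol and SAP*

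**What the plan says.** Section 12, Specific Aim #2, states the hypothesis in the singular: "The threshold for the positive effects will be between 0.0125 to 0.1 mg/70 kg, for the negative/aversive effect it will be" at or above 0.1 mg/70 kg.

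The Aim 2 Analysis then measures each construct with a pair of items. Positive effects rest on what it calls "main dependent variables of scores on the 'like the drug' and 'want more drug' items", each rated 0-100. For the other construct, "The negative aversive effects of nicotine will be determined by the 'dislike the drug' and 'lightheaded/dizzy' item of the DEQ".

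The Aim 2A method is "similar to the analysis described for Specific Aim #1A except that the dependent variables will be continuous". The Aim 1A rule is: "The lowest nicotine dose that has a significantly higher proportion of NSA than 0.5 will be selected as the threshold dose (Hypothesis 1A"). For Aim 2 the plan adds that "the mean ratings at each dose will be compared to 0".

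Two other places bear on this. The Drug Effects Questionnaire entry in section 11C lists five items: drug strength, good effects, bad effects, liking and head rush. Of the four Aim 2 items, only liking is among them. The sample size rationale in section 12 refers to a third pairing, good effects and drug liking.

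**The concern.** A lowest-significant-dose rule applied to two outcomes gives two thresholds. Suppose liking first reaches significance at 0.1 mg and wanting more at 0.2 mg. The first supports the positive limb of Hypothesis 2A and the second refutes it. The plan does not say which counts, so the choice can be made once both results are known.

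The Hypothesis 2B models have the same gap. They take positive (or negative) subjective effects as the predictor, in one model for each construct, and so need one score per construct. None is defined.

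**Working it through.** **The plan's own figure.** The rationale gives a detectable effect of 0.34 SD with 72 subjects, 80% power and two-sided alpha 0.05. For a one-sample test of a mean against 0:
- Normal approximation: (1.960 + 0.842)/√72 = 0.330.
- Noncentral t: detectable effect 0.335; power at 0.34 is 81.2%.

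The figure reproduces for a single variable. It does not cover a verdict drawn from two.

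**Simulation inputs.** From the documents: five doses (0.0125, 0.025, 0.05, 0.1, 0.2 mg/70 kg), 72 subjects, and the lowest-significant-dose rule. Assumed, because the documents give nothing: ratings are saline-subtracted, both items have the same true dose curve, test statistics correlate 0.4 across doses, and the two items correlate 0.85 to 0.5. Each z statistic has mean (effect in SD) × √72. A dose is significant if z exceeds 1.994, the two-sided 5% t cut-off on 71 degrees of freedom. There were 200,000 runs per setting.

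**Scoring.** Positive limb: supported if the threshold is 0.0125 to 0.1 mg; refuted if it is 0.2 mg or none is found. Aversive limb: supported if the threshold is 0.1 mg or higher, or none is found.

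| True effects at the five doses (SD) | Items give opposing positive verdicts | Items give opposing aversive verdicts |
|---|---|---|
| 0.10, 0.20, 0.34, 0.50, 0.60 | about 1% | 11-19% |
| 0.05, 0.10, 0.20, 0.40, 0.50 | 6-10% | 19-34% |
| 0.05, 0.10, 0.20, 0.34, 0.50 | 11-19% | 19-34% |
| 0, 0.05, 0.10, 0.20, 0.34 | 19-34% | 12-21% |

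The lower end of each range is inter-item correlation 0.85, the upper end 0.5.

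**What the unwritten rule is worth.** On the last curve the positive limb is supported in 54-62% of trials if either item suffices, and in 35-28% if both must agree.

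**False positives at one null dose.** At cut-off 1.994 a single item has a one-sided rate of 2.3%. The chance that at least one of two items exceeds it is 3.5% at correlation 0.85 and 4.2% at 0.5.

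**Effect of averaging.** The SD of a mean of two equal-variance items is √((1 + r)/2) of one item's SD: √(1.85/2) = 0.962 and √(1.5/2) = 0.866, so 4-13% smaller. If both items respond equally, the detectable shift falls from 0.34 to 0.34 × 0.962 = 0.33, or 0.34 × 0.866 = 0.29, of an item SD.

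**The case against.** - **Effects may be larger than the weaker curves assume.** In the first preliminary study (26 smokers) all doses, including 0.1 mg, were rated more pleasurable than saline. If that was a paired test at 0.05, the observed effect at 0.1 mg was at least about 2.06/√26 = 0.40 SD. It is a selected estimate from different smokers, but it makes the 1% and 6-10% rows credible. This stands, and is why the whole range is shown.
- **Different thresholds are not in themselves a contradiction.** A reader might infer that Hypothesis 2A is in conflict whenever the items disagree on the dose, which happens in roughly 30-56% of simulated trials. The documents do not support that: two thresholds both inside 0.0125 to 0.1 mg agree on the positive limb.
- **The written test may not be the one simulated.** Raw ratings from 0 to 100 cannot be negative. Compared literally with 0, both items would tend to be significant at every dose and so agree. Saline subtraction is plausible from the preliminary-study figure caption, but the Aim 2 text does not state it.
- **Bonferroni.** Section 12 applies it to post-hoc tests and secondary analyses, and section 4 names only self-administration outcomes as main, so Aim 2 may be covered. It would change the cut-off but would not say which item decides.
- **The choice does not always favour the hypothesis.** A reader might infer that taking whichever item is significant first always helps. On the aversive limb, where a high threshold is predicted, that rule works against Hypothesis 2A.
- **The pairing may not survive.** If the section 11C list governs, only bad effects is plainly aversive and head rush is ambiguous, so the aversive construct may have a single item.

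**Conclusion.** The gap is real on the text alone: one predicted threshold per construct, two items analysed, and no rule for which decides. It leaves an after-the-fact choice in the 2A verdict and an undefined predictor in 2B. Conflict is possible, not certain. Under the stated assumptions the positive limb is contradictory in about 1% of trials with strong effects and up to 34% with 0.20 SD at 0.1 mg; the aversive limb in roughly 11-34%. If the two items truly have different curves, conflict could be more frequent. Aim 1 is unaffected. The point merits correction before unblinding, but does not show that the trial will contradict itself.

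**What to change.** First reconcile the DEQ items in section 11C, the Aim 2 Analysis and the sample size rationale. Then, before unblinding, state one deciding variable per construct, used for both the 2A threshold and the 2B predictor:
- **Positive effects:** the mean of the two items, or one named item.
- **Aversive effects:** one named item. Disliking is evaluative and lightheadedness somatic; their dose curves may differ, and averaging could dilute the more sensitive one.

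Report the remaining items descriptively. State also whether ratings are saline-subtracted before comparison with 0.

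The cost is SAP wording, with no extra subjects or data. Item-specific results lose confirmatory status. One deciding variable keeps the 0.05 test. Splitting alpha over two items (0.025 each) would instead raise the detectable effect from 0.335 to 0.370 SD and cut power at 0.34 SD from 81% to 72%.
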